4.2 Treatment Logistics and Accountability

4.2.1 Packaging, Labeling, and Storage

Intracanalicular dexamethasone insert must be stored in a secure area accessible only to the Investigator and their designee(s) and refrigerated and stored between 2°C and 8°C. Intracanalicular dexamethasone insert contains 0.4 mg dexamethasone and is designed to provide a sustained and tapered release of therapeutic levels of dexamethasone to the

ocular surface for up to 30 days. Dexamethasone is an anti-inflammatory 9-fluoro-glucocorticoid (also termed a glucocorticoid agonist) and is the active ingredient found in MAXIDEX® 0.1% (dexamethasone ophthalmic suspension), which contains approximately 50 µg of dexamethasone per drop.

Study inserts will be supplied in an unmasked fashion by Ocular Therapeutix in a sealed foil pouch containing one intracanalicular dexamethasone insert in a foam carrier.

Study inserts will be shipped to the site via overnight shipping using cold packs to maintain a temperature of 2° to 8° C. The Investigator, or an approved representative (e.g. pharmacist), will ensure that all study drug inserts are stored in a secured area, under recommended storage conditions and in accordance with applicable regulatory requirements. The shipping box is to be opened and stored immediately at the site in a refrigerator intended for investigational products at a temperature of 2° to 8°C.

When the insert is removed from the refrigerator, it should be visually inspected. Exposure of the insert to temperatures outside these limits is not recommended. Records of actual storage conditions (i.e. temperature log) at the study site must be maintained; and must include a record of the dates, when the refrigerator was checked, the initials of person checking, and the temperature.

4.2.2 Supply and Disposition of Treatments

Study insert will be shipped at a temperature of 2° to 8°C to the investigator by sponsor as needed during the study.

4.2.3 Treatment Accountability

All study insert accountability records will be kept current.

The investigator will account for all opened and unopened packaging of study inserts. These records will contain the dates, quantity, and study medication

- Inserted in each patient,
- disposed of at the site or returned to Ocular Therapeutix

All accountability records will be made available for inspection by regulatory agency inspectors.

4.3 Concomitant Medications and Procedures

At the discretion of their physician, patients may continue to receive all medications and standard treatments administered for other conditions.

4.4 Potential Risks of Study

Steroids are known to increase eye pressure, which might be a finding of glaucoma, which is a vision threatening disease if not treated appropriately and promptly. In order to detect this, eye pressure will be checked at every visit as explained in sections: Schedule of Events (5.1), Study procedures (5.1.1), and rescue medications (5.2).

Additionally, steroids may mask signs of and enhance or and exacerbate the severity of ocular bacterial, viral, and fungal infections. The use of ocular steroids may slow the rate of ocular healing.

5. STUDY SCHEDULE OF EVENTS AND VISIT DESCRIPTIONS

5.1 Schedule of Events

Study assessments and procedures are presented by visit in Table 1

Table 1 Schedule of Events

Procedure	Run In* (Day -14 to -7)	Visit 1* (Day 1)	Visit 2 (Day 14)	Visit 3 (Day 28)	Visit 4 (Day 42)	Early Termination
Informed Consent	X	X**				
Inclusion/Exclusion/Demographics	X	X**				
Medical history and concurrent illnesses	X	X**				
Concomitant medications	X	X	X	X	X	X
Pregnancy Test		X			X	X
Log/Dispense Rescue Meds	X	X	X	X	X	
Insert Study Drug/Control		X				
BSCVA		X			X	X
VAS	X	X		X	X	X
Schirmer (W/O anesthesia)	X	X			X	X
OSS (corneal and conjunctival)	X	X	X	X	X	X
IOP	X	X	X	X	X	X
SLE	X	X	X	X	X	X
Dilated Fundus Exam	X	X**			X	X
Rescue med recording	X		X	X	X	X
AE recording		X	X	X	X	X

*If no run-in required, patient will start at baseline visit/ Day 1

**Required in absence of run-in visit

After having obtained an informed consent patients will be assigned a unique patient number and undergo the below procedures in the order they are listed.

1. Medical History and Review of Systems
 - i. Contact lens and glasses wearing (contact lens wear has to be discontinued 1 week prior and for the duration of the study)
 - ii. Current eye drops used:
 - a. Patients who are on dry eye drops, such as artificial tears, cyclosporine, or lifitigrast treatment will be eligible as long as the doses have been stable for at least 3 months
 - b. Patients who are on steroid drops will be placed in a 14 day wash-out period, in both eyes, before they can be eligible. If in the discretion of the principle investigator, discontinuation of the topical treatment could pose any harm to the patient's ocular health, the patient will be excluded.
 - c. Patients who are on anti-histamines, oral (doxycycline or azithromycin) or topical antibiotics (bacitracin or erythromycin ointment) are eligible for as long as the doses have been stable in the past 2 weeks

- d. Patients who are on oral steroids or other anti-inflammatory or immunomodulatory medications are eligible for as long as the doses have been stable in the past 3 months
- e. Patients using glaucoma drops in either eye will be excluded (with the exception of rescue medication)

iii. Current systemic medications (see above)

iv. History of eye diseases and previous eye or eyelid surgery

- a. Patients who had eye surgery in the past 3 months prior to study are ineligible
- b. Patients who had penetrating corneal transplantation are not eligible
- c. Patients who had endothelial corneal transplantation are eligible as long as the surgery was 3 months or longer ago

v. History of other inflammatory or autoimmune medical disease (GVHD, RA, SLE, etc), in particular presence of SS (primary or secondary), and related symptoms.

- a. These patients are eligible as long as they do not have cicatrizing conjunctivitis (such as SJS, MMP, etc)

2. Informed consent

Informed consent will be given to the patient to review at the time of approach in the clinical setting, or sent to the patient's home if identified via chart review. The patient will be given ample time to review the consent form, and will return on the day of the study visit with any questions. All questions will be answered and a discussion will be had with the person obtaining consent prior to the consent form being signed.

3. Pregnancy test

A standard urine pregnancy test provided by Ocular Therapeutix will be performed on women of childbearing potential at Baseline and Exit visit. A positive test will exclude patient from enrollment into the study as well as will be considered a serious adverse event if occurred during the study period.

4. Dry eye symptoms as measured using Visual Analog Scale (VAS).

Patients will complete VAS questionnaires for each eye in regard to eye dryness, eye discomfort, and eye fatigue. The most bothersome symptoms will be determined (of the three symptoms) at baseline and used throughout the study as the main symptom.

Patients will be given the questionnaire and expected to complete on their own. Help may be given to patients who have difficulty reading or understanding of the definition of the questions which will accompany the three questions.

The patient marks on the line the point that they feel represents their perception of their current state at each visit.

The VAS score is determined by measuring in millimeters using a ruler from the left hand end of the line (0) to the point that the patient marks, to a maximum 100.

5. Visual acuity (VA)

Distance visual acuity will be measured under monocular conditions using the subjects' habitual correction for distance (if wearing). The Snellen Chart will be used. If less than 20/20, pt will have Best Spectacle Corrected Visual Acuity (BSCVA) measured via Manifest Refraction.

6. Schirmer's test without anesthesia.

This test involves placing a small piece of filter paper against the conjunctiva for 5 minutes to observe how much tear volume is being produced in the temporal part of the lower cul-de-sac. The filter paper is removed after 5 minutes, and the length of the paper wetted is measured to approximate tear production. The testing will be performed as minimally disturbing to the ocular surface as possible. Time will be recorded if Schirmer's are completely saturated prior to the 5 minutes.

7. Ocular surface staining (OSS).

- i. Corneal fluorescein staining: About 2.5 minutes after instillation of the fluorescein eye drops (one drop of saline placed on the commercially available fluorescein strips) the staining will be scored according to the criteria published by SICCA (11).
- ii. Conjunctival lissamine green staining: Within 1 minute after instillation of lissamine green eye drops (one drop of saline placed on the commercially available strips) the staining will be scored. Conjunctival staining will be measured based on SICCA criteria (11).

8. Dilated Fundus Examination (DFE)

1 drop of Tropicamide 1% and Phenylephrine 2.5% will be used in each eye for purpose of dilation. Macula, blood vessels and cup to disk ratio will be recorded.

9. Insertion of study drug.

Treatment eye will be randomized by a Randomization list made by the Biostat Center at Johns Hopkins School of Medicine (using REDcap database) contralateral eye of each patient will serve as the control

The Treatment Physician will place the study device and contralateral plug/sham treatment at Day 1. The Treatment or the Examining physician can do the baseline exam.

The Examining Physician will perform the study exams (Day 1 through 42) to preserve masking.

10. Unmasking procedures (Day 42 or for serious AE)

All tests require both eyes testing and will be performed in the right eyes first, then the left eyes.

5.1.1 Study Procedures

Patients will be instructed not to instill any eye drops one hour prior to any study visit.

SCREENING VISIT/RUN IN (Day -14 to -7) – Either Examining or Treating physician will perform.

The following information will be collected:

- Informed Consent
- Inclusion/exclusion
- Demographics
- Medical history and concurrent illnesses
- Concomitant medications
- Log/Dispense Rescue medications
- Ocular Surface Disease Index Questionnaire (OSDI)
- Schirmer test without anesthesia
- OSS (Corneal and conjunctival)
- Intraocular Pressure (IOP)
- Slit Lamp Examination (SLE)
- Dilated Fundus Exam (DFE)
- Rescue Med Recording

BASELINE VISIT (Day 1)- Treating Physician (Unmasked)

If run-in Visit was NOT performed:

- Informed Consent
- Inclusion/Exclusion
- Demographics

- Medical History and concurrent illnesses
- Dilated Fundus Exam (DFE)

Needed for all Baseline Day 1:

- Concomitant medications
- Urine Pregnancy Test
- Log/Dispense Rescue Meds
- Insert Study Drug/Control
- Best Corrected Spectacle Visual Acuity (BSCVA)
- VAS
- Schirmer without anesthesia
- OSS
- IOP
- SLE
- AE recording

VISIT 2 (14+/-3 days) – Examining Physician (Masked)

- Concomitant medications
- Log/Dispense Rescue Meds
- OSS
- IOP
- SLE
- Rescue med recording
- AE recording

VISIT 3 (28+/-3 days) – Examining physician (Masked)

- Concomitant medications
- Log/Dispense Rescue Meds
- VAS
- OSS
- IOP
- SLE
- Rescue med recording
- AE recording

VISIT 4 (42+/-3 days) – Examining Physician

- Concomitant Medications
- Log/Dispense Rescue Meds
- Pregnancy Test
- BSCVA
- VAS

- Schirmer W/O anesthesia
- OSS
- IOP
- SLE
- Dilated Fundus Exam
- Rescue med recording
- AE recording

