DOSE/ROUTE/SCHEDULE:	Each patient's right eye will be randomized to receive either the treatment or the control. The left eye will automatically receive the alternative. For example if the right eye of the patient gets randomized to receive the study medication, left eye will automatically be the control eye. If the right eye gets randomized to receive the control treatment, the left eye will receive the study medication.
	Control eye will receive a sham treatment: commercially available tear duct plug without the dexamethasone (Vera90TM EXTENDED WEAR SYNTHETIC ABSORBABLE PUNCTAL PLUG made of E-Caprolactone-L-Lactide copolymer (PCL). Absorbs in 60 to 180 days. Size 0.5mm which is comparable to the study treatment)
	RESCUE MEDICINE: In patients with worsening of signs or symptoms, topical loteprednol 0.5% (Lotemax) drops up to 4 times a day, mimicking the usual practice, can be used at the discretion of the principle investigator.
	In patients with increased intraocular pressure (more than 5 points greater than baseline or more than 5 points higher than the fellow eye) treatment with topical beta blocker/betaxolol 0.5% (Betoptic) drops can be used 2 times a day to bring down the pressure at the discretion of the principle investigator.

Endpoint(s)

PRIMARY EFFICACY: Efficacy will be measured at 28 days.)

We have two co-primary end points:

- 1- Dry eye Sign: Corneal staining score measured using OSS scale on Day 28. The difference between the average corneal staining in the treated arm versus the average corneal staining in the sham arm will be compared statistically.
- 2- Patient reported symptom: Most bothersome symptom (any one of the (1)eye dryness, (2)eye discomfort, or (3)eye fatigue will be established as the most bothersome symptom at baseline for each eye) measured using visual analogue scale (0 to 100). The difference between the average most bothersome symptom in the treated arm versus the average most bothersome symptom in the sham arm will be compared statistically.

Secondary Efficacy:

We have two secondary end points:

- 1- Corneal staining responder analysis. Responder is defined as one full severity grade improvement in corneal staining. The percentage of subjects achieving 1 severity grade improvement in corneal staining (responders) in the treated arm versus sham arm will be compared statistically.

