1.2 Rationale

Previous studies showed that dexamethasone and loteprednol topical drops have led to favorable results (4-7). However, the requirement of frequent instillation of drops by the patients is problematic causing discomfort and blurring of vision and requires remembering and dexterity for instillation, poor compliance is not uncommon (7). In addition we believe that instillation of drops disturbs the homeostasis of the natural tear film due to physical and chemical trauma due to large drop volume (50 microliters) hammering on the eye surface (which can only hold 7 to 10 microliters). Particularly washing away of the mucin layer that holds all the “good ingredients” in the tears is harmful to the ocular surface. Therefore, “dropless” treatment of dry eye is desirable.

Dextenza® (dexamethasone ophthalmic insert, Ocular Therapeutix Inc., Bedford, MA) is a corticosteroid intracanalicular insert approved by US-FDA in November 2018 for the treatment of post-surgical ocular inflammation and pain. It is inserted into the lower lacrimal punctum and into the canaliculus. A single insert releases a 0.4 mg dose of dexamethasone for up to 30 days following insertion. Dextenza® is resorbable and does not require removal. We hypothesize that Dextenza® could mimic short-term topical steroid use in a tapering manner in patients with clinically significant dry eye and show efficacy in improving its symptoms and signs, as was previously shown with other steroid preparations. If proven, the use of Dextenza® may shift paradigms in the management of the clinically significant ocular surface disease. To test this hypothesis, we propose to study the effects of Dextenza® in the treatment of clinically significant dry eye. This proposal has several strengths over a non-masked protocol:

- 1- We have identified a tear duct plug with a comparable size (size 0.5mm) that lasts 60-180 days (Vera90TM). This would serve as an excellent comparison to Dextenza and allow the study to be a double-masked design. Both devices are not visible at the slit-lamp once inserted.
- 2- The investigator enrolling the patient (inserting the study treatment versus the control treatment) will be different than the examining investigator for each patient to allow the study to be truly double masked.
- 3- Because each patient will have one Dextenza eye and one control eye, the efficacy and safety of the treatment will be fairly, effectively, and accurately assessed. The

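### In patients with a one-sided pressure rise or one-sided rescue, the masked staining grader can receive a cue to which eye has the steroid before the Day 28 co-primary grade

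*Combined protocol and SAP*

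**What the plan says.** **Who does what.** Section 5.1.1 heads the follow-up visits "VISIT 2 (14+/-3 days) – Examining Physician (Masked" and "VISIT 3 (28+/-3 days) – Examining physician (Masked". Both lists contain concomitant medications, rescue logging and dispensing, OSS, IOP, slit-lamp examination, rescue recording and adverse events; Day 28 adds VAS. In both, the medication and rescue logs stand before OSS, while IOP and rescue recording stand after it. Section 5.1, item 9, states: "The Examining Physician will perform the study exams (Day 1 through 42) to preserve masking". No separate IOP assessor is named.

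**Allocation.** It is within patient. The Synopsis says of the randomised pair: "The left eye will automatically receive the alternative". Section 1.2 presents this as a strength: "Because each patient will have one Dextenza eye and one control eye".

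**Links between finding and arm.** Section 4.4 says "Steroids are known to increase eye pressure" and provides for pressure checks at every visit. Section 5.2 gives high IOP as an example of harm from the treatment and worsening dry eye as an example of harm from the control. One of the Synopsis triggers for pressure-lowering drops compares an eye with its fellow.

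**Safeguards.** Section 1.2 gives two. The inserting investigator "will be different than the examining investigator for each patient to allow the study to be truly double masked". On appearance, it says "Both devices are not visible at the slit-lamp once inserted".

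**The concern.** The two safeguards deal with how the devices look and who inserts them. Neither deals with what the examiner learns afterwards. The plan gives the grader the measurements most likely to differ between a steroid eye and a plug eye, and in a paired design a cue about one eye is a cue about both.

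Corneal staining at Day 28 is a co-primary endpoint. It is graded by one person at the slit lamp, right eye and then left. Appendix 1 uses dot-count bands plus extra points for confluence, pupillary staining and filaments, so some judgement remains. An expectation about which eye is treated could push the two grades apart, and that would pass straight into the treated-minus-sham difference. The secondary staining responder endpoint, with a threshold of one grade, would be exposed in the same way.

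**Working it through.** The documents give no figure for this risk, so there is none to reproduce. The check has two parts: which routes are open on the text, and how large the effect could be on assumed inputs.

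**1. Routes to the grader before the Day 28 grade**

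| Information | When | Before the Day 28 OSS? |
|---|---|---|
| Day 14 IOP, each eye | Visit 2, masked examiner | Yes |
| Rescue logged at Day 14 | Visit 2, masked examiner | Yes |
| High IOP at an unscheduled visit (5.1.2) | Between visits | Yes, if the examiner sees it |
| Day 28 medication and rescue logs | Visit 3, listed before OSS | Yes, if list order is followed |
| Day 28 IOP and rescue recording | Visit 3, listed after OSS | No, if list order is followed |
| Visit 4 findings | Day 42 | No |

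One-sided pressure-lowering treatment points towards the steroid eye. One-sided dry eye rescue points towards the plug eye, by the association in 5.2.

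**2. How informative is a one-sided rise?** Let pt and pc be the chances of a noticeable rise in the steroid and plug eye, taken as independent. Both are assumed.

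- P(one-sided rise) = pt(1 − pc) + pc(1 − pt)
- P(raised eye is the steroid eye) = pt(1 − pc) / [pt(1 − pc) + pc(1 − pt)]

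For pt = 5% and pc = 1%: 0.0495 + 0.0095 = 0.059, or about 5.0 of 85 patients, and 0.0495/0.059 = 0.84.

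With pc held at 1%:

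| pt | Patients of 85 with a one-sided rise | P(raised eye is the steroid eye) |
|---|---|---|
| 2% | 2.5 | 0.67 |
| 5% | 5.0 | 0.84 |
| 10% | 9.2 | 0.92 |
| 20% | 17.5 | 0.96 |

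Over pt from 2% to 20% and pc from 0.2% to 3%, the probability runs from 0.40 to 0.99. It exceeds 0.50 whenever pt > pc.

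**3. Effect on the staining comparison.** Inputs: 85 pairs (section 4.1); an assumed SD of the paired difference of 1.5 grades; an assumed share of patients revealed, f; an assumed shift in the drug's favour, b; and a normal paired test, since the plan names no test.

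- SE = 1.5/√85 = 0.163
- Shift in the mean difference = f × b
- One-tail false-positive risk = 1 − Φ(1.96 − shift/SE)

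| f | b | Shift | Shift/SE | Risk |
|---|---|---|---|---|
| none | – | 0 | 0 | 2.5% |
| 5% | 0.5 | 0.025 | 0.154 | 3.5% |
| 10% | 1 | 0.10 | 0.615 | 8.9% |
| 15% | 1 | 0.15 | 0.922 | 15% |

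For the 0.10 shift, the two-sided rate goes from 5.0% to 9.4%. With an SD of 1 or 2 instead, it is 15.2% or 7.5%.

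**4. Allowing for wrong guesses.** The table takes every revealed guess as correct. If the grader shifts towards whichever eye is raised, wrong guesses offset right ones and the net shift is b × (pt − pc). With pt = 10%, pc = 1% and b = 1, that is 0.09. Then 0.09/0.163 = 0.55, and the risk is 1 − Φ(1.96 − 0.55), about 8.0%. When pt is well above pc, the correction is small.

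**The case against.** **The cue is not proof.** A reader might infer that a one-sided rise identifies both eyes. The documents do not support that. A plug eye can also read higher, and the dry eye rescue drug in the Synopsis is itself a topical steroid that could raise pressure in a plug eye. This objection stands: the cue suggests allocation and does not establish it.

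**It may be rare.** Section 4.1.2, item 12, excludes patients with a history of steroid response, which lowers the number of rises, and no rate is given. This stands. Most patients may give no cue at all.

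**The list order partly protects already.** OSS is listed before IOP and before rescue recording, so a reader who infers that the grader is meant to see Day 28 pressure first would be wrong. But the order in 5.1.1 is not stated to be binding, and its Day 1 list puts insertion ahead of VAS and OSS, so the lists look like checklists. Section 5.1 does prescribe an order for its numbered procedures, but neither IOP nor the rescue log is among them. The protection is therefore only implied, and it does not cover Day 14, unscheduled visits or the logs that precede OSS.

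**Some links are inferred.** No passage says that pressure-lowering drops go to one eye only; the fellow-eye trigger merely makes it plausible. Rescue is at the principal investigator's discretion, and the documents do not say whether that person is the grader. Both points stand.

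**The size is assumed.** The SD, the share revealed and the shift are all assumptions, and a full-grade shift in every revealed patient is a strong one given the dot-count bands. A mean shift of 0.10 is only 3.3% of the planned 3-point difference (0.10/3). This stands as to size. The test, however, is against zero, so a small systematic shift still raises the false-positive risk.

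**Conclusion.** The masking gap is real but conditional. On the text, the masked grader is assigned the rescue and medication logs and IOP at Days 14 and 28, the paired design makes a cue about one eye a cue about both, and neither written safeguard covers this route.

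It affects only patients with a one-sided pressure rise or one-sided rescue before the Day 28 grade. It does not show that the trial is unmasked as a whole, and Visit 4 plays no part because it follows the primary grade. On the assumed inputs, the one-tail false-positive risk for the staining comparison rises from 2.5% to between about 3.5% and 15%. That range is an illustration, not an estimate: the documents give neither the rate of asymmetry nor the SD of the paired difference. It also concerns the staining test alone, not a joint decision on both co-primaries. The correction is worth making because it is cheap and precedes the grade on which a co-primary result rests.

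**What to change.** 1. In 5.1.1, Visits 2 and 3, require VAS (where scheduled) and OSS to be completed and locked in the database before the examiner opens the concomitant medication and rescue logs or measures IOP. This makes the existing OSS-before-IOP listing a rule and moves the logs after the grade.
2. Keep IOP and rescue entries from earlier scheduled and unscheduled visits off the grading form until the lock.
3. Add a sensitivity analysis of Day 28 staining without patients who had asymmetric IOP or one-sided rescue before Day 28. Fix the definition of asymmetry before unmasking. Removing a patient removes both eyes, so the pairing is kept. But rescue may itself reflect response, so this analysis should support the main one and not replace it.
4. State as a limitation that the same examiner may recall Day 14 findings. Locking within a visit cannot remove that. A separate IOP assessor would reduce it, but needs extra staff.

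The cost is reordered forms, a short delay before the logs are opened and one added analysis. No staff or procedures are added. IOP and rescue information is fully available at the same visit once the grade is locked, and the rescue and safety rules are unchanged.
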